10.2.8 Collection and Reporting of AEs, SAEs, and Abnormal LFTs

10.2.8.1 Collection Period

Collection of AEs (ie, AEs, SAEs, and Abnormal LFTs) will commence at the time the participant signs the informed consent. Routine collection of AEs will continue until the follow-up phone call on Day 14 ± 2 days after the soticlestat dose. For participants who discontinue prior to the administration of study medication, AEs will be followed until the participant discontinues study participation.

10.2.8.2 Reporting AEs

At each study visit, the Investigator will assess whether any subjective AEs have occurred. A neutral question, such as “How have you been feeling since your last visit?” may be asked. Participants may report AEs occurring at any other time during the study. Participants

experiencing an SAE prior to the exposure to investigational product must be monitored until the symptoms subside and any clinically relevant changes in laboratory values have returned to Baseline or there is a satisfactory explanation for the change. Nonserious AEs that begin prior to the exposure to investigational product, related or unrelated to the study procedure, need not be followed-up for the purposes of the protocol.

All participants experiencing AEs, whether considered associated with the use of the study medication or not, must be monitored until the symptoms subside and any clinically relevant changes in laboratory values have returned to Baseline or until there is a satisfactory explanation for the changes observed. All AEs will be documented in the AE page of the CRF, whether or not the Investigator concludes that the event is related to the drug treatment. The following information will be documented for each event:

- Event term.
- Start and end date and time.
- Pattern of AE (frequency).
- Severity/Intensity.
- Causality (Investigator's opinion of the causal relationship between the event and administration of study drug[s]).
- Action taken with study drug.
- Outcome of event.
- Seriousness.

10.2.8.3 Reporting SAEs

When an SAE occurs through the AE collection period it should be reported according to the procedure outlined below.

A Takeda SAE form must be completed, in English and signed by the Investigator immediately or within 24 hours of first onset or notification of the event. The information should be completed as fully as possible but contain, at a minimum:

- A short description of the event and the reason why the event is categorized as serious.
- Participant identification number.
- Investigator's name.
- Name of the study medication(s).
- Causality assessment.

The SAE form should be transmitted within 24 hours to the attention of the contact listed in Appendix 14.1.1.

Any SAE spontaneously reported to the Investigator following the AE collection period should be reported to the Sponsor if considered related to study participation.

Reporting of SAEs that begin before administration of investigational product will follow the same procedure for SAEs occurring on treatment.

10.2.8.3.1 SAE Follow-Up

If information is not available at the time of the first report becomes available at a later date, the Investigator should complete a follow-up SAE form or provide other written documentation and fax it immediately within 24 hours of receipt. Copies of any relevant data from the hospital notes (eg, ECGs, laboratory tests, discharge summary, postmortem results) should be sent to the addressee, if requested.

All SAEs should be followed up until resolution or permanent outcome of the event. The timelines and procedure for follow-up reports are the same as those for the initial report.

10.2.8.4 Reporting Special Interest AEs

Not Applicable.

10.2.8.5 Reporting of Abnormal LFTs

Healthy Participants Only

If a participant is noted to have ALT or AST elevated $>3 \times \text{ULN}$ on 2 consecutive occasions, the abnormality should be recorded as an AE. In addition, an LFT Increases CRF must be completed providing additional information on relevant recent history, risk factors, clinical signs and symptoms and results of any additional diagnostic tests performed.

If a participant is noted to have ALT or AST $>3 \times \text{ULN}$ and total bilirubin $>2 \times \text{ULN}$ for which an alternative etiology has not been identified, the event should be recorded as an SAE and reported as per Section 10.2.8.3. The Investigator must contact the Medical Monitor for discussion of the relevant participant details and possible alternative etiologies, such as acute viral hepatitis A or B or other acute liver disease. Follow-up laboratory tests as described in Section 10.0 must also be performed. In addition, an LFT Increases CRF must be completed and transmitted with the Takeda SAE form (as per Section 10.2.9).

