4.2 Rationale for the Proposed Study

In this study, the impact of HI on the PK of single dose soticlestat [REDACTED]. After entering the body, drugs are eliminated by excretion and/or metabolism. Although elimination can occur through a variety of routes, most drugs are cleared by metabolism in the liver and/or small intestine and/or by elimination of unchanged drug by the kidney. Liver disease is associated with several pathophysiologic changes that may alter the PK of a drug. These include alterations in hepatic blood flow, changes in liver enzyme activity, decreased binding of drug to plasma proteins, and impaired biliary excretion [2, 3]. Accordingly, current United States (US) FDA guidance recommends a PK study in patients with impaired hepatic function if hepatic metabolism and/or excretion accounts for a substantial portion ($\geq 20\%$ of the absorbed drug) of the elimination of a parent drug or active metabolite [4].

The magnitude of the effect of mild, moderate, or severe HI on the PK of soticlestat was assessed based on model-based simulations of HI effect using in vitro enzyme phenotyping data and data from the human ADME study. The simulations suggested that in participants with mild, moderate, or severe HI, soticlestat AUC_{∞} is expected to be 1%, 23%, and 33% higher, respectively, than healthy participants with normal hepatic function; soticlestat C_{max} is expected to be 0%, 6%, and 7% higher, respectively, compared with healthy participants with normal hepatic function.

Based on model-based simulations, this study first evaluated the PK in participants with moderate HI (n=8) and healthy matched participants with normal hepatic function (n=12) and an interim PK analysis was conducted. The interim analysis indicated higher impact of moderate HI on soticlestat PK than the model predicted. For participants with moderate HI, soticlestat PK exposure increased to 214.93%, 316.47%, and 299.38% for C_{max} , AUC_{last} , and AUC_{∞} , respectively, when compared to the respective PK exposure in matched participants with normal hepatic function. As a result, this study will further evaluate the impact of mild HI on the PK of soticlestat. In addition, the Sponsor decides not to dose participants with severe HI. Soticlestat will not be recommended to use in subjects with severe HI.

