5.2.2 Study Secondary Objective

- To evaluate the safety and tolerability of soticlestat following a single oral dose in participants with moderate or mild HI as well as matched healthy participants with normal hepatic function.

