This study will investigate the impact of impaired hepatic function on the plasma PK of soticlestat [REDACTED] and safety compared to matched healthy participants with normal hepatic function in order to provide dosing recommendations to clinicians for future treatments of soticlestat to patients with varying degrees of HI. An informal interim PK data analysis was performed following soticlestat administration in participants with moderate HI ($n=8$) and healthy matched participants with normal hepatic function, which has demonstrated higher than expected soticlestat exposure in participants with moderated HI than in healthy matched participants with normal hepatic function. The Sponsor has decided not to recommend soticlestat dosing in patients with severe HI, therefore participants with severe HI will not be enrolled in the current study. Instead, this study will enroll an arm of participants with mild HI in order to further investigate the impact of HI on soticlestat PK. Due to the variability of soticlestat PK and easier accessibility of healthy participants in comparison to participants with HI, an increased number of healthy participants will be enrolled.

The Child-Pugh classification will be used to categorize HI due to its widespread use and acceptance by regulatory agencies (including the FDA). It has been shown to correlate with hepatic (ie, metabolic) clearance for several compounds [4]. In the current study, participants with chronic, stable HI with features of cirrhosis due to any etiology will be enrolled using the

Child-Pugh scale. The scale employs five clinical measures of liver disease listed in [Table 6.a](#). Each assessment is scored 1 - 3, with 3 indicating most severe derangement. Participants' scores of 5 to 6, 7 to 9, and 10 to 15 on this scale are classified as having mild, moderate, and severe HI, respectively.

Table 6.a Derivation of Child-Pugh Classification Score¹

Parameter	1 point	2 points	3 points
Serum albumin (g/dL)	>3.5	2.8 to 3.5	<2.8
Total serum bilirubin (mg/dL)	<2.0	2.0 to 3.0	>3.0
Prothrombin time (PT) (second prolonged) or International normalized ratio (INR) (ratio)	<4 <1.70	4 to 6 1.70 to 2.30	>6 >2.30
Ascites	Absent	Slight	Moderate or participants on medication to control ascites
Hepatic encephalopathy grade	None	Grade 1 or 2	Grade 3 or 4 or participant receiving medication(s) to prevent encephalopathy

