7.1.2 Inclusion for Healthy Participants

Participants must fulfill the following inclusion criteria to be eligible for participation in the study:

1. Is an adult male or female participant aged ≥ 18 to < 75 years, at screening. Healthy participants will be matched to hepatic impaired participants in this study by sex (± 2 per sex) and by age (mean ± 10 years).
2. Has a BMI ≥ 18.0 and ≤ 40.0 kg/m², at screening. At least 50% of the participants will be required to be of BMI ≥ 18.0 and ≤ 35.0 kg/m², at screening. Healthy participants will be matched to hepatic impaired participants in this study by BMI (mean $\pm 10\%$).
3. Medically healthy with no clinically significant medical history, physical examination, laboratory profiles, vital signs or ECGs, as deemed by the Investigator or designee.
 - Supine BP is $\geq 90/40$ mmHg and $\leq 150/95$ mmHg, at screening;
 - Supine PR is ≥ 40 bpm and ≤ 99 bpm, at screening;
 - QTcF is ≤ 450 msec (males) or ≤ 470 msec (females) and ECG findings considered normal or not clinically significant by the Investigator or designee, at screening;
 - Liver function tests including ALT, AST, ALP and total bilirubin \leq the ULN at screening and check-in.
4. Participants should not have renal dysfunction as demonstrated by a relatively adequate renal function (creatinine clearance ≥ 60 mL/min), at screening.

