6.7.3 Clinical Laboratory Assessments

Hematology, serum chemistry, coagulation, and urinalysis will be performed at screening, Day -1, Day 3, and Day 7 (or at ET if applicable). Urine drug screening will be carried out at screening and Day-1 only. For female participants, a pregnancy test will be performed at screening and check-in and FSH will be checked at screening. In addition, laboratory safety tests may be performed at various unscheduled time points, if deemed necessary by the Investigator.

For all laboratory values that are numeric, summary statistics (n, mean, SD, minimum, median, and maximum) will be presented for each laboratory test by hepatic function group (ie, Severe HI, Moderate HI, Mild HI, Normal Hepatic Function) and time point of collection. Change from baseline will be summarized in a similar manner. Baseline is defined as the last assessment, including recheck and unscheduled assessments, taken prior to dosing. All clinical laboratory listings and tables will be presented in international system (SI) units. Postdose unscheduled or recheck assessments will not be used in analysis. Similarly, ET results will not be included in summaries.

For calculation of summary statistics, lab results below or equal to lower limit of quantification (LLOQ) will be set to LLOQ/2 if a LLOQ value has been defined, and otherwise will be set to missing; lab results above or equal to upper limit of quantification (ULOQ) will be set to ULOQ

if a ULOQ value has been defined, and otherwise will be set to missing. Listings will display the original result received from the laboratory.

Out-of-normal range flags will be recorded as follows: high (H) and low (L) for numerical results and did-not-match (*) for categorical results. For each laboratory test, a shift table will be developed comparing the frequency and percentage of the results at baseline (above normal (H), normal (N), or below normal (L)) with the postdose time points. For urinalysis tests, the categories are normal (N) and abnormal (A). Out-of-range values and corresponding recheck results will be listed.

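### No liver-test threshold for recording AEs or SAEs applies to the hepatic impairment arms, and the SAP's laboratory tables do not make up for it

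*Protocol*

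**What the plan says.** - **Objective and endpoints.** Protocol 5.2.2: "To evaluate the safety and tolerability of soticlestat following a single oral dose in participants with moderate or mild HI", together with matched healthy participants. Protocol 5.3.2 measures this by TEAE incidence and by the incidence of clinically significant abnormal values.
- **Reporting rule.** Protocol 10.2.8.5, under "Healthy Participants Only": ALT or AST above 3 × ULN on two consecutive occasions is an AE and needs an LFT Increases CRF. With ALT or AST above 3 × ULN and total bilirubin above 2 × ULN "for which an alternative etiology has not been identified, the event should be recorded as an SAE", with Medical Monitor contact.
- **Rules that cover every arm.** Protocol 7.5 calls for clinical follow-up at ALT or AST above 8 × ULN, or above 5 × ULN with listed symptoms or signs. Protocol 10.1 lets the investigator record a laboratory change judged clinically significant, and asks for worsening of a pre-existing condition to be recorded as an AE. Table 10.a counts hepatic necrosis and acute liver failure as serious.
- **Entry.** Protocol 7.1.2 requires "Liver function tests including ALT, AST, ALP and total bilirubin" at or below ULN in healthy participants. Protocol 7.1.1 sets no such ceiling for HI.
- **SAP laboratory outputs.** SAP 6.7.3 has a shift table "comparing the frequency and percentage of the results at baseline (above normal (H), normal (N), or below normal (L)) with the postdose time points". It also summarizes each numeric test by group and time point with n, mean, SD, minimum, median and maximum, and says "Change from baseline will be summarized in a similar manner". Post-dose unscheduled, recheck and early-termination (ET) results stay out of the summaries.
- **Promised and dropped items.** Protocol 11.1.5.2 leaves the laboratory markedly abnormal value (MAV) criteria to the SAP. SAP 6.7.3 contains none. SAP 8.0 drops the separate analysis of clinically significant abnormal values because AE reporting is said to cover it.

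**The concern.** TEAE incidence is tabulated side by side for the HI and normal-function groups. Such a table is readable only if the same finding has a similar chance of becoming a TEAE in each group. For liver tests the healthy arm has a numeric rule and the HI arms have none, so a lower count of hepatic TEAEs in HI could reflect the drug, the missing threshold, or both.

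The laboratory tables would normally give a check that does not depend on what investigators chose to record. Here SAP 8.0 sends abnormal values back to AE reporting, which has no numeric liver criterion in HI, and the remaining tables are weakest for participants who start above normal. Exposure adds to the interest: Protocol 4.2 reports moderate-HI exposure at about 2.1 (Cmax), 3.2 (AUClast) and 3.0 (AUC∞) times that of matched controls at the interim.

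**Working it through.** The plan states no figure on this point, so there is none to reproduce. The check sets the rules side by side, asks whether a raised baseline is possible, and traces a case through the outputs.

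**1. Rules by arm**

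| Provision | Healthy | HI | Numeric? | Makes it an AE/SAE? |
|---|---|---|---|---|
| Protocol 10.2.8.5 | yes | no | yes | yes |
| Protocol 7.5 | yes | yes | yes (ALT/AST only) | no, follow-up only |
| Protocol 10.1, laboratory changes | yes | yes | no | if judged clinically significant |
| Protocol 10.1, worsening of a pre-existing condition | yes | yes | no | yes, once worsening is recognized |
| Protocol Table 10.a | yes | yes | no | yes, but for severe liver events |

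Meeting 7.5 does not by itself create an AE: it asks for follow-up including repeat tests, and 10.1 says a re-test or continued monitoring is not an intervention. The HI arms hold 8 + 8 = 16 participants out of 16 + 12 = 28 to 16 + 24 = 40, or 40% to 57%.

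**2. Can an HI participant start above normal?** Table 6.a scores bilirubin 1 point below 2.0 mg/dL, 2 points at 2.0 to 3.0 and 3 points above 3.0. I enumerated all combinations of the five items scored 1 to 3:

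- Score 5–6 (mild): 6 combinations, of which 1 has bilirubin at 2 points and none at 3.
- Score 7–9 (moderate): 90 combinations, of which 45 have bilirubin at 2 points or more and 15 at 3 points.

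These count combinations, not expected participants. The documents give no bilirubin ULN. Assuming 1.0 to 1.5 mg/dL, any value of 2.0 or more is already high, so raised baselines are possible in both HI arms. ALT and AST are not Child-Pugh items and have no numeric entry ceiling in HI.

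**3. An illustrative case** (values chosen for illustration; no symptoms and no other cause found). An HI participant goes from ALT 1.5 to 4.8 × ULN and from bilirubin 1.2 to 2.4 × ULN.

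- Change from baseline: 4.8/1.5 = 3.2-fold and 2.4/1.2 = 2.0-fold.
- 10.2.8.5: 4.8 > 3 and 2.4 > 2, so a healthy participant with these post-dose values has an SAE. The rule does not apply to HI.
- 7.5: 4.8 < 5 and 4.8 < 8, so it is not met.
- Shift table: high to high for both tests. A healthy participant, who must enter at or below ULN, would read normal to high.

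**4. What the SAP would still show.** A rise at a scheduled visit can appear as the maximum change for that test, group and time point. All values are listed by participant under SAP 6.7, including rechecks, unscheduled and ET results. If the peak falls at an unscheduled, recheck or ET assessment, it appears in no summary.

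**5. What eight participants can show.** With zero events in n, the one-sided 95% upper bound is 1 − 0.05^(1/n): 31.2% for n = 8, 22.1% for n = 12 and 11.7% for n = 24.

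**The case against.** The strongest reply is that nothing is hidden. Worsening of a pre-existing condition is recordable as an AE in every arm, and that standard already refers to the participant's own state. Protocol 10.2.8.2 requires monitoring until laboratory changes return to baseline or are explained. The maximum change from baseline is tabulated, and with eight participants per HI arm each course can be read from the listings. All of this stands. A reader might infer that hepatic worsening in HI can go unreported; the documents do not support that. What is missing is a numeric recording threshold and a summary, not a reporting route or the data.

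A restriction to healthy participants is also understandable. Under the ULN assumption above, 2 × ULN is 2.0 to 3.0 mg/dL, so a Class B participant above 3.0 mg/dL exceeds the bilirubin limb before dosing. Chronic liver disease is also an obvious alternative cause. The illustrative case is not fully like for like either: from a baseline at or below ULN, the same ALT is at least a 4.8-fold rise. This could explain why the rule was not copied to HI, although the documents give no reason. It does not explain why the SAP has no baseline-relative output instead.

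A reader might also apply the interim exposure increase to both HI arms. It was observed in moderate HI only; no mild-HI result is given, and the model predicted 1% higher AUC∞ and no change in Cmax there.

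**Conclusion.** The point holds in a limited form. For 16 of the 28 to 40 planned participants, recording hepatic worsening as an AE or SAE rests on investigator judgement and general AE wording, with a follow-up rule that has no bilirubin limb and no recording instruction. TEAE incidence is therefore ascertained under different rules by arm. The SAP does not compensate, because of the high/normal/low categories, the excluded values, the absent MAV criteria and the dropped abnormal-value analysis. SAP 8.0 does not list the MAV omission as a change.

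The size cannot be put as a bias in TEAE incidence: the documents give no event rates, and the number of participants who start above normal is unknown. The conclusion assumes only that some HI participants have raised liver tests at baseline, which the entry criteria permit.

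A reader might go on to say that the safety objective is least answerable in the HI arms. The documents do not establish that. The safety evaluation is descriptive, with no hypothesis or decision rule, and zero events in eight leaves a 31.2% upper bound whatever tables are used.

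**What to change.** **In the SAP:**

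1. In 6.7.3, for ALT, AST, ALP, total bilirubin, INR and albumin, add a table by hepatic function group of each participant's worst post-dose value relative to own pre-dose baseline (lowest for albumin, highest for the others). Apply it identically to all arms. SAP 6.7.5 already sets baseline against worst post-baseline and worst change for QTcF, and that layout can be reused. State that unscheduled, recheck and ET values count for this table, since the general rule excludes them. The ratios can be summarized and shown individually, so the table needs no clinical cut-off.
2. Supply the laboratory MAV criteria promised in Protocol 11.1.5.2, with baseline-relative categories, or list their omission with a reason in SAP 8.0.

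**In the protocol:** the sponsor should reconcile 7.5, 10.1 and 10.2.8.5 and decide whether the HI arms need their own reporting threshold. None is proposed here. Any such change would reach only participants not yet dosed. The moderate HI arm was evaluated before this amendment, so a new rule would itself make ascertainment differ between the two HI arms. The SAP table avoids this because it can be applied to all dosed participants.

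**Cost:** one extra safety table with small numbers per arm, and the work of writing the MAV criteria. The tests are already taken at screening, Day -1, Day 3 and Day 7 or ET, so no new samples are needed.

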10.2.9 Safety Reporting to Investigators, IRBs or IECs, and Regulatory Authorities

The Sponsor will be responsible for reporting all suspected unexpected serious adverse reactions (SUSARs) and any other applicable SAEs to regulatory authorities, Investigators and IRBs or IECs, as applicable, in accordance with national regulations in the countries where the study is conducted. Relative to the first awareness of the event by/or further provision to the Sponsor or Sponsor's designee, SUSARs will be submitted within 7 days for fatal and life-threatening events and 15 days for other serious events, unless otherwise required by national regulations. The Sponsor will also prepare an expedited report for other safety issues where these might materially alter the current benefit-risk assessment of an investigational medicinal product or that would be

sufficient to consider changes in the investigational medicinal products administration or in the overall conduct of the study. The investigational site also will forward a copy of all expedited reports to his or her IRB or IEC in accordance with national regulations.

